5.1 Study Drug Dosing

Study Drug Dosing for the UX001-CL201 feeder study and for this study UX001-CL202 are mapped to present all possible treatment combinations that a subject may participate in within these two studies (Table 3).

Table 3 Study Drug Dosing Pathways: UX001-CL201 – UX001-CL202

Path	UX001-CL201		UX001-CL202	
	Weeks 0-24	Weeks 24-48	Part I	Part II
1	6g/day	6g/day	6g/day	12g/day
2	3g/day	3g/day	6g/day	12g/day
3	0g/day	6g/day	6g/day	12g/day
4	0g/day	3g/day	6g/day	12g/day
5	N/A	N/A	N/A	12g/day

The 0/6 and 0/3 treatment groups (pathways 3 and 4) may be combined during weeks 0-24 for UX001-CL201 subjects to form a placebo group for comparisons with pathway 5.

The 0/6 and 6/6 treatment groups (pathways 1 and 3) and 0/3 and 3/3 treatment groups (pathways 2 and 4) may be combined to form 3g and 6g treatment groups for comparison with the 12g/day SA-ER/SA-IR dosing.

A total of 5 separate treatment pathways are identified for evaluation. Subjects enrolled in UX001-CL202 who are members of the TNP will have no treatment pathway from the UX001-CL201 study. Subjects who roll over from UX001-CL201 into Part I of this study will continue on a dose of 6g/day SA-ER. These data will be used primarily for additional safety data. All subjects participating in Part II of this study will receive 12g/day SA-ER/SA-IR. The focus of the safety analyses for the primary objective will be on safety at the 6g/day SA-ER and safety at the 12g/day SA-ER/SA-IR doses.

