6.5.8 Determination of Baseline Values

Multiple baseline values for efficacy endpoints will be considered for the planned analyses. [Figure 1](#) presents an analysis map that highlights the various possible baselines for planned analyses. [Table 3](#) presents a dosing pathway matrix for all subjects enrolled in the study. Each pathway can be associated with a different baseline for analysis summaries and comparisons.

In order to examine the long term trends and changes in SA therapy for those subjects who roll-over from UX001-CL201 additional analyses will also be performed using baseline assessments obtained at the following time points ([Figure 1](#)):

- UX001-CL201 6/6 and 3/3 rollover subjects: UX001-CL201 Week 0 Visit
- UX001-CL201 0/6 and 0/3 rollover subjects: UX001-CL201 Week 24 Visit
- UX001-CL201 0/6 + 6/6 rollover subjects: UX001-CL201 Week 48 Visit
- UX001-CL201 0/3 + 3/3 rollover subjects: UX001-CL201 Week 48 Visit
- UX001-CL201 All rollover subjects: UX001-CL201 Week 48 Visit

- UX001-CL201 All rollover subjects: UX001-CL202 Part I Termination Visit
- UX001-CL202 Treatment Naïve Subjects: UX001-CL202 Part II Screening/Baseline Visit (Week 0: Note that protocol refers to this as week 12 on the T&E schedule.)

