SA-ER	
the change from this score will be compared to the week 24 12g/day SA-ER/SA-IR treatment to assess the impact of the 12g/day SA-ER/SA-IR dose across the combined 3/3+0/3 dose (UX001-CL201 subjects treated with 0/3 or 3/3 SA-ER will be combined for comparison from dosing pathways 2 and 4 from Table 3)
 
A second comparison will be with a 6 minute walk test at Screening of ≥ 200 m (6MWT≥ 200m)

Secondary Analysis: Stability in endpoint over time and dose from Week 0 UX001-CL201 through Week 24 UX001-CL202. (Trend over time)
	
All subjects who roll-over from UX001CL201 will have their week 0 assigned as baseline and the stability from this baseline score will be assessed over time through the week 24 12g/day SA-ER/SA-IR treatment to assess the impact of dose combinations over time. For this analysis the UX001-CL201 subjects treated with 0/6 or 6/6 SA-ER will be combined for analysis from dosing pathways 1 and 3 and subjects treated with 0/3 or 3/3 SA-ER will be combined for analysis from dosing pathways 2 and 4 (Table 3). Each dosing pathway combination will be a separate analysis to assess the trend in endpoint scores over time and dose.
 
A second comparison will be with a 6 minute walk test at Screening of ≥ 200 m (6MWT≥ 200m)

Treatment Naïve Primary Analysis: Week 24 12g/day SA/ER/SA-IR vs. Week 0 Baseline (Week 12 on T&E)
	
Treatment Naïve subjects who enroll in UX001-CL202 will have a primary comparison of their change from baseline assessment for efficacy parameters.

Treatment Naïve Secondary Analysis: Week 24 12g/day SA/ER/SA-IR vs.
	
Treatment Naïve subjects in UX001-CL202

Planned Comparison	Description
Week 0-24 UX001-CL201 Placebo	endpoint data from week 0 to 24 will be compared to the UX001-CL201 Placebo (for those patients with 6MWT >=200m) treated subjects' endpoint data from week 0 to 24 for change from baseline assessments.

Additional comparisons may be defined upon review of the data to examine trends throughout a subject's treatment course through both UX001-CL201 and UX001-CL202, via the dosing pathways identified in [Table 3](#) and [Figure 1](#).

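### The SAP's Secondary Analysis follows 0/6+6/6 and 0/3+3/3 pools from UX001-CL201 Week 0, so the first 24 weeks of each pooled trend mix placebo with active drug

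*SAP*

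**What the plan says.** The Secondary Analysis row of SAP Table 8 (section 6.7.1) is titled "Stability in endpoint over time and dose from Week 0 UX001-CL201 through Week 24 UX001-CL202". Four statements in the row define it.

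- Baseline: "All subjects who roll-over from UX001CL201 will have their week 0 assigned as baseline and the stability from this baseline score will be assessed".
- First pool: "For this analysis the UX001-CL201 subjects treated with 0/6 or 6/6 SA-ER will be combined for analysis from dosing pathways 1 and 3".
- Second pool: "subjects treated with 0/3 or 3/3 SA-ER will be combined for analysis from dosing pathways 2 and 4".
- Unit of analysis: "Each dosing pathway combination will be a separate analysis to assess the trend in endpoint scores over time and dose".

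The row is repeated in subjects who walked at least 200 m at Screening.

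SAP section 5.1 (Table 3) gives 0 g/day for pathways 3 and 4 in Weeks 0-24. The text below that table recognises this, for the comparison with pathway 5: "The 0/6 and 0/3 treatment groups (pathways 3 and 4) may be combined during weeks 0-24 for UX001-CL201 subjects to form a placebo group". The next sentence permits the other grouping: "0/3 and 3/3 treatment groups (pathways 2 and 4) may be combined to form 3g and 6g treatment groups for comparison with the" 12 g/day regimen.

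SAP section 6.5.8 lists baselines by group. For the placebo starters it has "UX001-CL201 0/6 and 0/3 rollover subjects: UX001-CL201 Week 24 Visit". The 6/6 and 3/3 groups have Week 0, and the pooled pairs have Week 48.

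**The concern.** The row is meant to show whether an endpoint stays stable across time and dose. Labelling subjects by their Weeks 24-48 dose while starting the clock at Week 0 puts untreated person-time inside a curve that will be read as a dose group. Section 5.1 calls these pools the 3 g and 6 g groups.

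If subjects on placebo lose strength, that loss appears as part of the trend on drug. SAP 6.7.6 itself allows for decline during the placebo period. If the placebo starters then stabilise or improve once treated, the pooled slope changes at Week 24 although nothing changed for the active starters. A reader could not tell a time effect or a dose effect from this change in the pool's exposure.

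**Working it through.** No power or sample-size figure is attached to this analysis, so there is nothing to reproduce. The check is a reading of the dosing table plus a mixture calculation.

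**1. Dose inside each pool (SAP Table 3)**

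| Pool | Weeks 0-24 | Weeks 24-48 |
|---|---|---|
| Pathways 1+3 (6/6 and 0/6) | 6 g/day and 0 g/day | 6 g/day in both |
| Pathways 2+4 (3/3 and 0/3) | 3 g/day and 0 g/day | 3 g/day in both |

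The exposure mismatch is confined to Weeks 0-24. The Week 0 in this row is that of UX001-CL201, as the row title states. It is not the Part I termination visit that Primary Analysis #1 calls week 0.

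**2. Effect on the pooled change**

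Let p be the share of the pool that started on placebo, A the mean Week 24 change in active starters and P that in placebo starters.

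- Pooled Week 24 change = (1 - p) x A + p x P.
- Pooled minus active-starter change = -p x (A - P).

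At a later visit t, with baseline still at Week 0:

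- Pooled change = (1 - p) x A(t) + p x [P + R(t)], where R(t) is the change in placebo starters after they begin drug. The term p x P stays in every later value.

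The documents give about 46 rollover subjects but no count per pathway, so p is an assumption. If UX001-CL201 had allocated 1:1:1 and split placebo equally between 3 g and 6 g, p would be 0.5/(1 + 0.5) = 1/3.

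| Assumed p | Shift, as a share of (A - P) | Mean assigned dose, Weeks 0-24: 1+3 pool, 6 x (1 - p) | 2+4 pool, 3 x (1 - p) |
|---|---|---|---|
| 0.20 | 20% | 4.8 g/day | 2.4 g/day |
| 1/3 | 33% | 4.0 g/day | 2.0 g/day |
| 0.50 | 50% | 3.0 g/day | 1.5 g/day |

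**3. The bend at Week 24**

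Take A = 0 and P = -1 unit, with no change in anyone once on drug. Active starters are flat throughout. With p = 1/3 the pooled curve falls to -0.33 at Week 24, then runs flat and stays at -0.33 at every later visit. Both the fall and the bend come only from the placebo starters.

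**4. Baselines side by side**

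| Group | SAP 6.5.8 | Table 8 Secondary Analysis |
|---|---|---|
| 6/6 and 3/3 | Week 0 | Week 0 (inside a pool) |
| 0/6 and 0/3 | Week 24 | Week 0 (inside a pool) |
| Pooled pairs | Week 48 | Week 0 |

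Section 6.5.8 lists no Week 0 baseline for a pooled pair.

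**5. Model**

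The general covariates in section 6.7.2 are baseline value, gender and age. No term for starting arm or pathway is named.

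**6. Planned output**

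Tables 15 to 506 in SAP 8.1 number 506 - 15 + 1 = 492. At 12 per endpoint that is 41 endpoints. Each has two Secondary Analysis tables, giving 41 x 2 = 82.

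**The case against.** The strongest reply is that the SAP does not rely on this row alone.

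- Section 6.5.8 announces additional long-term analyses with Week 0 for active starters and Week 24 for placebo starters.
- Section 6.7.4 plans scatter plots for every endpoint, colour-coded by pathway.
- Section 6.7.6 plans further analyses of the HHD composites by pathway or combinations of pathways.
- The Treatment Naïve Secondary Analysis still uses the UX001-CL201 placebo period as comparator.

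All of this stands. A reader might infer that this is the only planned analysis of the whole treatment course, or that the placebo period is lost from the plan. Neither is so. But none of these items changes what the 82 tables will show.

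Three other strong readings are tempting and fail.

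- **A diluted test.** One could say that the 6 g versus placebo or 6 g versus 3 g difference at Week 24 shrinks by the factor 1 - p. The row makes no such contrast; each pool is its own within-group trend. What is displaced is the trend.
- **A flat contradiction.** Sections 5.4 and 6.5.8 say that several baselines will be used, and section 5.1 permits both groupings. Different groupings for different questions are not contradictory. The weakness is the combination of a pooled pair with a Week 0 baseline.
- **Pooling makes no sense before Week 48.** Both members of each pool are on the same dose from Week 24. Prior exposure differs after that, but it also differs at Week 48 (24 versus 48 weeks), where the SAP pools. The reason to keep the pools at Week 48 is that section 6.5.8 assigns them that baseline.

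**Conclusion.** The point holds for this row of Table 8. As written, each pooled Week 0-24 trend mixes placebo and active subjects, every later change from Week 0 carries the placebo-period change, and a bend at Week 24 may only reflect placebo starters beginning drug. Stability over time and dose cannot be read cleanly from those curves.

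The size is p x (active - placebo), or 20% to 50% of that gap for p from 0.20 to 0.50. Both p and the gap are unknown from the documents. Protocol 7.4.3 reports almost no effect at 3 g, so the distortion is likely to be larger in the 6 g pool. If active and placebo changes were equal at Week 24, there would be no shift there.

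The importance is moderate. This is a secondary trend in an open-label study that SAP 6.1 says is not powered for statistical comparisons. A reader might infer that the primary results are affected too, but Primary Analyses #1 to #3 start from the Part I termination visit or UX001-CL201 Week 48 and count no placebo time.

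**What to change.** Reword the Secondary Analysis row of Table 8 in one of two ways.

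- **By pathway.** Run the trend for pathways 1, 2, 3 and 4 separately from UX001-CL201 Week 0, and mark Weeks 0-24 of pathways 3 and 4 as placebo.
- **By time since first sialic acid dose.** Use the section 6.5.8 baselines (Week 0 for 6/6 and 3/3, Week 24 for 0/6 and 0/3) and show the placebo period separately. On this clock placebo starters reach 12 g/day 24 weeks sooner, if Part I lasts equally long, so the start of 12 g/day must be marked for each group.

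In either case, state that placebo and active person-time will not be pooled from a Week 0 baseline. Keep the 0/6+6/6 and 0/3+3/3 pairs for analyses with the Week 48 baseline that section 6.5.8 gives them. Report the number of subjects per pathway.

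The cost is one reworded row and reprogramming of its tables, on data already held. The groups become smaller and the intervals wider, in a set of about 46 rollover subjects.

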Evaluations of safety, changes in clinical endpoints such as muscle strength, mobility, and function, and changes in exploratory serum biomarkers will be performed according to the Schedule of Events specific to each phase of the study ([Table 2.1](#) and [Table 2.2](#)). A Termination Visit will be conducted 4 weeks after subjects receive their last dose of study drug (last dose of study drug received at Month 36). For subjects who are eligible and choose to participate in the UX001-CL302 open-label extension study, the Month 36 Visit is considered the end of study visit and the Termination Visit is not required. Any subject who discontinues the current study early or is ineligible or decides not to participate in the UX001-CL302 open-label extension study is required to have a Termination Visit 4 weeks after their last dose of study drug, as per Schedule of Events. Efficacy data analyses will be conducted at the end of the Treatment Period, although interim analyses may be performed at the discretion of Ultragenyx.

Safety will be monitored throughout the study based on physical examinations, clinical laboratory analyses, and reporting of adverse events (AEs) and Serious Adverse Events (SAEs). An independent Data Monitoring Committee (DMC) will review safety information periodically on an ad hoc basis as outlined in the DMC charter, which is maintained separately from this protocol.

NUMBER OF SUBJECTS PLANNED:

Up to 46 subjects previously treated in the UX001-CL201 study will be enrolled. Approximately 10 subjects, naïve to SA and MaNAc treatment, will be enrolled directly into Part II of the study.

DIAGNOSIS AND CRITERIA FOR INCLUSION AND EXCLUSION:

Individuals eligible to participate in this study must meet all of the following criteria:

- Enrollment in, and successful completion of the UX001-CL201 protocol **OR**
(for 10 treatment naïve subjects):
 - Have a confirmed diagnosis of GNE Myopathy
 - Aged 18 -65 years of age, inclusive
 - Able to walk ≥ 200 meters and < 80% of predicted normal during the 6MWT (orthotics and assistive devices allowed)
 - No prior history of treatment with SA or MaNAc
- Must be willing and able to provide written, signed informed consent after the nature of the study has been explained, and prior to any research-related procedures
- Must be willing and able to comply with all study procedures
- Sexually active subjects must be willing to use an acceptable method of contraception while

participating in the study

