7.3 Selection of Study Population

The study will be conducted in adult patients who have previously demonstrated mutations in the gene for the GNE/MNK enzyme leading to a diagnosis of GNE myopathy (variously termed HIBM, DMRV, or Nonaka disease). These patients are unable to synthesize endogenous SA, which leads to muscle weakness and atrophy. Consequently, this is the relevant population for testing SA replacement therapy to determine if exogenous SA leads to improved protein and lipid sialylation and stabilized or improved muscle structure and performance. The majority of the study population will consist of approximately 46 GNE Myopathy subjects who successfully completed UX001-CL201 and may or may not have

been previously exposed to SA-ER. Approximately 10 GNE Myopathy subjects who are SA and MaNAc-treatment naïve will be enrolled into Part II of the study.

The inclusion/exclusion criteria from the UX001-CL201 study inherently define the study population for subjects in Part I of the study, since successful completion of UX001-CL201 is requisite for enrollment in this study. The previous study was designed to allow for the enrollment of patients with a broad spectrum of physical disability, with at least 60% of enrolled subjects having residual lower extremity strength and function sufficient to walk ≥ 200 meters in the 6MWT. Enrolling patients across the spectrum of disease severity as subjects allowed the study to fully explore the safety and efficacy profile of SA-ER and inform the design of future studies. However, it should be noted that subjects unable to complete UX001-CL201 would not be eligible for this extension study, potentially introducing population bias toward subjects experiencing favorable safety and efficacy following up to 48 weeks treatment with SA-ER.

For the additional treatment naïve subjects enrolled into Part II of the study, the diagnosis and age range are the same as requirements for continuing subjects. This subgroup will be restricted to GNE Myopathy subjects with the ability to walk at least 200 meters during the 6MWT. Since the strongest clinical efficacy signal was observed in this subset of GNE Myopathy subjects participating in the UX001-CL201 study, this protocol was designed to enroll those subjects most likely to obtain clinical benefit from study treatment.

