7.6.1.1 Clinical Efficacy Analyses

All subjects with any post-dose data will be included in the intent-to-treat (ITT) efficacy analysis.

Efficacy will be evaluated by continued improvement in clinical assessments. Efficacy assessments may differ depending on the phase of the study (i.e., Part I, Part II, Part III, or

Part IV). For Part I efficacy evaluation, results from the last pre-treatment assessment from UX001-CL201 will be compared with the last post-treatment assessment for the Part I Treatment Period as listed in the Schedule of Events ([Table 2.1](#)), with efficacy conclusions based on change since SA-ER treatment initiation. An interim analysis will be conducted when a majority of subjects have completed the Month 6 Visit of the Part II Treatment Period. For Part II efficacy evaluation of the continuing subjects, change from baseline of Part II to Month 6 assessment at 12g/day SA-ER/SA-IR dose will be determined and compared with the improvement observed during the first 6 months of treatment with 6 g/day SA-ER dose, and to the rate of change observed with placebo or 3g treatment during the first 6 months of the study.

The changes from baseline of the treatment-naïve subjects will be evaluated over time. Potential comparisons of the changes from baseline to Month 6 will be performed for the 6MWT, UE, and LE between the naïve group versus the placebo and 6g/day treatment groups for the first 24 weeks of treatments in subjects able to walk more than 200m at baseline. In addition, changes in muscle strength over the entire treatment period of subjects who started with 6g/day and 3g/day will be evaluated and compared to the projected values of subjects who received placebo for the first 24 weeks of treatment in UX001-CL201.

A full accounting of the analyses for Parts III and IV of the study will be provided in the Statistical Analysis Plan.

For those clinical evaluations with repeated assessments (i.e., HHD, 6 MWT, walking speed and weighted arm lift tests) the analysis will be performed using a repeated measures analysis. An exchangeable variance-covariance structure will be used. The final treatment effect estimate based on this model will be the estimated treatment difference at Month 36. The purpose of including data from assessments prior to Month 36 is to increase the precision of the estimated variance, while using categorical effects of time-by-treatment to avoid modeling assumptions.

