3 STUDY DESIGN

As background for the statistical methods presented below, this section provides an overview of the study design and plan of study execution. The protocol (plus protocol amendment) is the definitive reference for all matters discussed in what follows.

UX001-CL202 open-label extension study will assess the long term safety and efficacy of SA ER/SA-IR treatment over a period of approximately 36 months, or until marketing approval or program termination by Ultragenyx. In Part I of the study, approximately 46 subjects will be enrolled following successful completion of the UX001-CL201 study. The Baseline visit will be conducted in conjunction with the UX001-CL201 Week 48 study visit to avoid treatment disruption. Enrollment will take place after all UX001-CL201 Week 48 study assessments have been completed and the investigator has determined the subject meets all eligibility criteria. Data collected at the UX001-CL201 Week 48 visit will serve as the Baseline data for Part I of this protocol. Following the signing of informed consent at the Baseline visit, each subject will be dispensed a 6-week supply of study drug. Throughout the Part I Treatment Period of the study, all subjects will continue to take four 500 mg SA-ER tablets orally three times per day (TID), in the morning, early evening, and at bedtime (qHS), for a total dose of 6g/day. The Part I Termination Visit will also serve as the Baseline Visit for Part II of the study. However, for completion of the analysis with integrated information from UX001-CL201 subjects the baseline may be defined as the week 48 visit from UX001-CL201, or other such baselines from key time points in the UX001-CL201 study as may be defined for selected analyses to examine clinical endpoints.

Beginning with the Part II-Baseline Visit, all subjects currently enrolled in Part I will crossover to the SA-ER/SA-IR dosing regimen. An additional 10 treatment naive GNE Myopathy subjects will be enrolled into Part II of the study. The additional subjects will provide an assessment of SA-ER/SA-IR treatment in SA naïve subjects able to walk at least 200 meters (and < 80% predicted) in a screening 6 Minute Walk Test (6MWT). Throughout the 36-month Part II Treatment Period, all subjects will be administered 1.5g SA-ER and 1.5g SA-IR orally four times per day (QID), in the morning, afternoon, early evening, and qHS, for a total SA dose of 12g/day.

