171	HHD Upper Extremity CS- Summary
172	HHD Upper Extremity CS- Primary Analysis #1
173	HHD Upper Extremity CS- Primary Analysis #1- 6MWT >= 200
174	HHD Upper Extremity CS- Primary Analysis #2
175	HHD Upper Extremity CS- Primary Analysis #2- 6MWT >= 200
176	HHD Upper Extremity CS- Primary Analysis #3
177	HHD Upper Extremity CS- Primary Analysis #3- 6MWT >= 200
178	HHD Upper Extremity CS- Secondary Analysis
179	HHD Upper Extremity CS- Secondary Analysis- 6MWT >= 200
180	HHD Upper Extremity CS- Treatment Naïve Primary Analysis
181	HHD Upper Extremity CS- Treatment Naïve Secondary Analysis
182	HHD Upper Extremity CS- Treatment Naïve Secondary Analysis- 6MWT >= 200
183	HHD Lower Extremity CS- Summary
184	HHD Lower Extremity CS- Primary Analysis #1
185	HHD Lower Extremity CS- Primary Analysis #1- 6MWT >= 200

Table ID⁽¹⁾	Table Description⁽²⁾
186	HHD Lower Extremity CS- Primary Analysis #2
187	HHD Lower Extremity CS- Primary Analysis #2- 6MWT >= 200
188	HHD Lower Extremity CS- Primary Analysis #3
189	HHD Lower Extremity CS- Primary Analysis #3- 6MWT >= 200
190	HHD Lower Extremity CS- Secondary Analysis
191	HHD Lower Extremity CS- Secondary Analysis- 6MWT >= 200
192	HHD Lower Extremity CS- Treatment Naïve Primary Analysis
193	HHD Lower Extremity CS- Treatment Naïve Secondary Analysis
194	HHD Lower Extremity CS- Treatment Naïve Secondary Analysis- 6MWT >= 200
195	6MWT- Summary
196	6MWT- Primary Analysis #1
197	6MWT- Primary Analysis #1- 6MWT >= 200
198	6MWT- Primary Analysis #2
199	6MWT- Primary Analysis #2- 6MWT >= 200
200	6MWT- Primary Analysis #3
201	6MWT- Primary Analysis #3- 6MWT >= 200
202	6MWT- Secondary Analysis
203	6MWT- Secondary Analysis- 6MWT >= 200
204	6MWT- Treatment Naïve Primary Analysis
205	6MWT- Treatment Naïve Secondary Analysis
206	6MWT- Treatment Naïve Secondary Analysis- 6MWT >= 200
207	Comfortable Gait Speed- Summary

Table ID⁽¹⁾	Table Description⁽²⁾
208	Comfortable Gait Speed- Primary Analysis #1
209	Comfortable Gait Speed- Primary Analysis #1- 6MWT >= 200
210	Comfortable Gait Speed- Primary Analysis #2
211	Comfortable Gait Speed- Primary Analysis #2- 6MWT >= 200
212	Comfortable Gait Speed- Primary Analysis #3
213	Comfortable Gait Speed- Primary Analysis #3- 6MWT >= 200
214	Comfortable Gait Speed- Secondary Analysis
215	Comfortable Gait Speed- Secondary Analysis- 6MWT >= 200
216	Comfortable Gait Speed- Treatment Naïve Primary Analysis
217	Comfortable Gait Speed- Treatment Naïve Secondary Analysis

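### The treatment-naïve versus CL201 placebo contrast does not apply the naïve walking limits to the comparator, so it is at risk of residual severity confounding, most clearly in 41 listed tables with no 6MWT limit

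*SAP*

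**What the plan says.** **Naïve entry.** The protocol (Synopsis and 7.3.1) sets two walking limits: "Able to walk ≥ 200 meters and < 80% of predicted normal during the 6MWT". SAP section 3 repeats both, describing "SA naïve subjects able to walk at least 200 meters (and < 80% predicted) in a screening 6 Minute Walk Test (6MWT".

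**Comparator.** The Treatment Naïve Secondary Analysis in SAP Table 8 (6.7.1) limits the CL201 placebo subjects by distance alone: "endpoint data from week 0 to 24 will be compared to the UX001-CL201 Placebo (for those patients with 6MWT >=200m". Protocol 7.6.1.1 also uses distance alone, taking the "first 24 weeks of treatments in subjects able to walk more than 200m at baseline". Neither applies a percent-predicted limit. SAP 5.1 says the two placebo-start pathways "may be combined during weeks 0-24 for UX001-CL201 subjects to form a placebo group for comparisons with pathway 5", and that sentence carries no walking limit.

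**Table list.** SAP 8.1 lists two versions of this contrast per endpoint. Table 181, for example, is "HHD Upper Extremity CS- Treatment Naïve Secondary Analysis", and Table 182 has the same title with a 6MWT >= 200 suffix.

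**CL201 population.** Protocol 7.3 says CL201 was designed with "at least 60% of enrolled subjects having residual lower extremity strength and function sufficient to walk" 200 m or more.

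**Covariates.** SAP 6.7.2 makes baseline value, gender and age general covariates where appropriate, and allows others that pass p < 0.05. Screening 6MWT distance is named in 6.7.7 and carried by reference into 6.7.8. Both sections concern 6MWT endpoints.

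**The concern.** Table 8 offers the naïve cohort no other comparison with untreated patients. The contrast is between studies and not randomised, so applying the same entry rule to both sides is one of the few protections available. The sponsor treats walking ability as relevant to outcome: Protocol 7.3 restricted naïve entry because the strongest CL201 signal was seen in those able to walk 200 m. If the two groups differ in walking severity and 24-week change depends on it, part of any difference credited to 12 g/day would be a difference in case mix.

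There is also a plain conflict in the plan. Table 8 and Protocol 7.6.1.1 define a comparator limited by distance, while the table list implies a second one without a limit. A programmer cannot tell from the SAP whether the unlimited version is intended or what standing its p-values have.

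**Working it through.** The plan gives no effect size, power or sample size for this contrast, so there is no figure of its own to reproduce.

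**1. The rules side by side**

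| Source | At least 200 m | Below 80% predicted |
|---|---|---|
| Naïve entry (Protocol 7.3.1, SAP 3) | yes | yes |
| Comparator, SAP Table 8 | yes | no |
| Comparator, Protocol 7.6.1.1 | yes (more than 200 m) | no |
| Pooled placebo, SAP 5.1 | not stated | not stated |
| Unsuffixed tables, SAP 8.1 | not in title | not in title |

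**2. Number of tables.** The endpoint tables run from ID 15 to 506 in blocks of 12: (506 − 15 + 1) / 12 = 492 / 12 = 41 endpoints. The last two lines of each block are the naïve-versus-placebo tables: 25, 37, …, 505 without the suffix and 26, 38, …, 506 with it. Every naïve subject walks at least 200 m at entry, so an unsuffixed table can differ from its partner only by admitting placebo subjects below 200 m.

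**3. Unsuffixed tables: size of the bias.** Unadjusted bias = (share of comparator below 200 m) × (difference in mean change between the strata). CL201's minimum of 60% walkers puts the share at up to 40%, assuming the all-arm figure holds in placebo. The stratum difference is not in the documents and is assumed to be 0.25, 0.5 or 1 SD:

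- 0.40 × 0.25 = 0.10 SD
- 0.40 × 0.5 = 0.20 SD
- 0.40 × 1 = 0.40 SD

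If the share is zero, so is the bias.

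**4. Effect on a two-sided 0.05 test.** Take 10 naïve subjects and n placebo subjects, with n assumed to be 10 to 20. SE = √(1/10 + 1/n), which is 0.447 SD at n = 10 and 0.387 SD at n = 20. False-positive rate = Φ(−1.96 − b/SE) + 1 − Φ(1.96 − b/SE):

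| Bias b | n = 10 | n = 20 |
|---|---|---|
| 0.10 SD | 0.056 | 0.058 |
| 0.20 SD | 0.073 | 0.081 |
| 0.40 SD | 0.145 | 0.178 |

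For scale, the difference detectable with 80% power is (1.96 + 0.84) × SE, about 1.25 SD at n = 10 and 1.09 SD at n = 20.

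**5. 200 m tables: the missing 80% limit.** The same formula applies. If 0 to 30% of placebo walkers are at or above 80% predicted and their change differs by 0.5 SD (both assumed), the bias is 0 to 0.30 × 0.5 = 0.15 SD.

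**6. What own-baseline adjustment removes.** This was checked by simulation with invented parameters. Walking ability is standard normal, the 200 m floor is at −0.25 SD, the 80% cap is at +1 SD, and change rises 0.5 SD per SD of walking ability.

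| Correlation of the endpoint's baseline with walking ability | Unrestricted comparator: unadjusted → adjusted | 200 m-only comparator: unadjusted → adjusted |
|---|---|---|
| 0.3 | 0.16 → 0.15 | −0.15 → −0.15 |
| 0.7 | 0.16 → 0.09 | −0.16 → −0.12 |
| 1.0 | 0.16 → 0.00 | −0.16 → 0.00 |

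Adjustment works fully only when the endpoint's own baseline captures walking severity. At a correlation of 0.7 it leaves 0.09/0.16 = 56% and 0.12/0.16 = 75% of the bias. The two mismatches act in opposite directions, so no overall sign can be claimed.

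**The case against.** A reader might infer that the contrast is confounded as a matter of fact, that CL201 placebo walkers at or above 80% predicted sit in the comparator, and that the bias is about 0.15 SD. The documents do not support that. CL201's entry criteria are not reproduced, so the number of such subjects is unknown and may be zero. Protocol 7.3 names only the 200 m floor when it describes how the naïve group is restricted, which leaves open whether CL201 already had a ceiling. The 30% and 0.5 SD inputs are assumptions. The evidence on walking ability concerns the treatment signal, not untreated change above and below 80%. This objection stands in full, so for the 200 m tables only a possible bias can be claimed.

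The second objection is that the SAP already adjusts. Baseline value, gender and age are general covariates, others may enter, and the 6MWT model contains distance, age and gender, which are the ingredients of percent predicted. That largely answers the point for the 6MWT endpoints. It answers less for endpoints whose own baseline tracks walking poorly. The CK model (6.7.13) names only time points, dose and baseline CK, and the free SA model (6.9.1) only its own baseline. Selecting covariates at p < 0.05 is a weak safeguard with about 10 naïve subjects.

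The third objection is that the unsuffixed tables look like mechanical expansion of a template. The list also gives 200 m versions of Primary Analysis #1, for which Table 8 describes none, and 8.1 leaves details to a separate specification. That is a fair reading of how the conflict arose, but the tables remain prospectively listed and SAP 6.5 attaches two-sided 0.05 tests generally.

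Finally, this is a secondary analysis in a study with no power claim, and the protocol calls the comparisons potential. The naïve primary analysis, change from own baseline, is unaffected. These facts limit the weight of the point without removing it.

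**Conclusion.** The contrast is at risk of residual severity confounding; confounding is not demonstrated. Two parts should be kept apart.

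- **Unsuffixed tables (41).** These conflict with Table 8 and Protocol 7.6.1.1, and the conflict stands whatever the size of the bias. That they lack a walking limit is inferred from their titles, but no other reading distinguishes them from their suffixed partners. The unadjusted bias is 0 to 0.40 SD, given a share below 200 m of up to 40% and stratum differences of up to 1 SD. The placebo share and the stratum differences are assumptions.
- **200 m tables (41).** The comparator lacks the naïve group's 80% limit. Whether this matters depends on CL201 data not given here, and the illustrative range of 0 to 0.15 SD starts at zero for that reason.

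These sizes are before adjustment and are small beside a detectable difference of roughly 1.1 to 1.25 SD. The case for change is that the correction is cheap and removes a possible bias that own-baseline adjustment need not remove.

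**What to change.** - In Table 8, define the comparator as CL201 placebo subjects whose Week 0 6MWT was at least 200 m and below 80% of predicted. Carry the same definition into SAP 5.1.
- Keep the protocol's 200 m-only comparator as a sensitivity analysis, so that the protocol's definition is still reported.
- Add baseline 6MWT (percent predicted or distance) as a prespecified covariate for this contrast on every endpoint whose model does not already contain it.
- Delete the 41 unrestricted naïve-versus-placebo tables, or label them descriptive and omit p-values.
- Report how many placebo subjects meet each rule.

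The cost is one filter, one covariate and an edit to the table list. The comparator may lose some subjects and intervals may widen slightly. The number lost cannot be computed from the documents. If no placebo walker is at or above 80% predicted, the new filter leaves the 200 m comparator unchanged.
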